Exposure to an acute stressor using a mental stress task normally increases urinary sodium excretion in the laboratory setting. However, there is substantial variability between individuals in the degree of stress-induced sodium excretion. Individuals with lower stress-induced sodium excretion who experience psychological stress during the daytime may exhibit a shift of urinary sodium excretion from the daytime to nighttime periods due to an inability to excrete additional sodium during the daytime. This abnormal *diurnal* pattern of urinary sodium excretion may, in turn, be associated with a smaller decline in BP from the daytime to nighttime periods, leading to reduced BP dipping and elevated nighttime BP. The overall goal of the proposed study is to examine the associations between psychological stress, the *diurnal* pattern of sodium excretion, and the *diurnal* pattern of BP. The aims of the study are:

Primary Aim 1: To examine the association between urinary sodium excretion after provoked psychological stress and the diurnal pattern of sodium excretion.

Primary Aim 2: To examine the association between the diurnal pattern of sodium excretion and the diurnal pattern of BP.

Two secondary or exploratory aims that will also be investigated:

Secondary Aim: To examine whether the association between urinary sodium excretion after provoked stress and the *diurnal* pattern of sodium excretion is modified by ecological momentary levels of perceived stress, experienced during the daytime period.

Exploratory Aim: To determine the sociodemographic, behavioral, and psychological traits, chronic stress, and biological stress-related factors that are associated with lower stress-induced sodium excretion. Identification of these factors will help determine who is at risk for having a differential sodium excretion response to psychological stress.

2. Study Design

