The study will be conducted both in the laboratory and in the naturalistic environment with a multiethnic sample of 211 adult community participants from upper Manhattan who do not have a history of *CVD, diabetes, chronic kidney disease, difficulty with blood draws,* or another *major medical condition* and are not taking antihypertensive medication. During a Laboratory Visit, urinary sodium excretion in response to mental stress tasks will be examined. Urinary volume, electrolytes, creatinine, and endothelin-1 will be measured at baseline, post-stress, and recovery; salivary cortisol will be measured at baseline and post-recovery; the urinary albumin-to-creatinine ratio will be measured at baseline; plasma angiotensin II and epinephrine/norepinephrine will be measured at baseline and post-stress, and a basic metabolic panel, a lipid panel, and a Hemoglobin A1c assessment will be used at the baseline only. Blood pressure and heart rate will be measured continually during the Laboratory Visit (every five minutes) and for the following 24 hours (every 30 minutes).

In the naturalistic environment, during the 24-hour period following the Laboratory Visit, the diurnal pattern of sodium excretion (measured during the daytime and nighttime) will be assessed by measuring urine volume and the urine concentrations of electrolytes and creatinine. Heart rate will be monitored using ABPM and ecological momentary assessments (EMA) of perceived stress will be surveyed.

The study has high clinical significance for improving our understanding of how psychological stress, sodium excretion and its *diurnal* pattern, and the *diurnal* pattern of BP are linked, and has the potential for identifying a treatment target to reduce the CVD risk associated with reduced BP dipping.

3. Study Procedures

a. Participant Engagement

Interested individuals will review an online information sheet and provide consent to participate in an electronic eligibility screen. This form will provide the contact information of the primary investigator, clinical research coordinator, and IRB office to ensure that all questions about the study, form, and participant's rights are answered before consent for screening is provided. Consent must be provided before access to the eligibility screen is allowed.

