Primary Aim 1: Standard regression analysis will be used. We will estimate the unadjusted relation of awake-to-sleep ratio of urinary sodium excretion rate to change in urinary sodium excretion rate with stress. Next, we have a priori selected the following covariates for adjustment in a multiple regression model: age, sex, race/ethnicity (non-Hispanic whites, non-Hispanic blacks, Hispanics, and other), and body mass index. Age, sex, and race/ethnicity are standard covariates in studies of hypertension given their well-known associations with BP. Body mass index is included as a covariate since it is associated with both lower stress-induced sodium excretion and lower day-to-night ratio of urinary sodium excretion rate. The statistical significance of the coefficient for the change in urinary sodium excretion rate with stress in this adjusted model will constitute the primary test of the hypothesis. Sensitivity analyses will be performed to assess whether the strength of the association changes when additional covariates are included. Higher clinic SBP/DBP and parental history of hypertension are associated with lower stress-induced sodium excretion. Fasting blood glucose and 24-hour creatinine clearance are associated with lower daytime-to-nighttime ratio of urinary sodium excretion rate. Each of these will be evaluated as candidate covariates by selecting those that are associated with the outcome (awake-tosleep ratio of urinary sodium excretion rate) at p<0.10. Finally, secondary analyses will use generalized additive models (GAM) to explore potential non-linearity of the relationship, using PROC GAM in SAS.

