Primary Aim 2: The same approach for Hypothesis 1 will be used for the analysis of this hypothesis. SBP dipping and DBP dipping will be the primary and secondary outcomes, respectively. The *a priori* covariates that will be included in adjusted models are: age, sex, race/ethnicity, body mass index, 24-hour sodium excretion, 24-hour potassium excretion, 24-hour creatinine clearance, FENa, current smoking, alcohol consumption, and fasting blood glucose. In addition to age, sex, and race/ethnicity (which were chosen because they are standard covariates in hypertension studies), the other measures were chosen as covariates as they may confound the association between the *diurnal* pattern of sodium excretion and the *diurnal* pattern of BP. Sensitivity analyses will be performed after additional covariates are included in the adjusted model. Prior studies have suggested that physical activity and fasting glucose are associated with the diurnal pattern of BP. Each of these measures will be evaluated as candidate covariates using the same approach described above for Primary Aim 1.

Sample Size and Minimum Detectable Effect Sizes for Primary Aims: The sample size for this study was selected to ensure 80% power to detect a bivariate/partial correlation between the primary predictor and outcome of r=0.20 or greater; this is conservative, but consistent with our preliminary data in which the correlation between the change in urinary sodium excretion rate with stress and awake-to-sleep

ratio of urinary sodium excretion rate (Primary Aim 1) was 0.25, and the correlation of awake-to-sleep ratio of urinary sodium excretion rate and SBP dipping (Primary Aim 2) was 0.30. The minimum sample size required to detect this effect size with power 80% is 194 with valid data for the three primary measures (change in urinary sodium excretion rate with stress, awake-to-sleep ratio of urinary sodium excretion, and SBP dipping). We are targeting a final minimum sample size with complete data of 200.

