Secondary Aim: The ecological stress level for the awake period during which participants' sodium excretion is monitored will be defined as the mean perceived stress level across the Ecologic Momentary Assessment (EMA) reports. Ecological stress is conceptualized as a moderating variable. Controlling for the effects of this measure and stress-induced sodium excretion, we will test their multiplicative interaction term; an extension of the regression model used to test Primary Aim 1. A positive interaction effect would provide the first empirical evidence supporting the conclusion that the hypothesized tendency for those with lower stress-induced sodium excretion rate to have a lower daytime-to-nighttime ratio of urinary sodium excretion rate is stronger among those who experience higher stress during the day of monitoring. Although a moderator is not required to be associated with the outcome, we will examine the association between mean perceived stress and daytime-to-nighttime ratio of urinary sodium excretion rate. In the SABRE pilot study, the correlation coefficient for this association was -0.42.

Exploratory Aim: Univariable and multivariable linear regression analyses will be performed to assess which factors are independently associated with lower stress-induced sodium excretion. All models will adjust for age, sex, and race/ethnicity. Variables entered into subsequent multivariable regression models will include other social determinants (place of birth, years living in the US, primary language spoke in the home, education attainment, employment status, health insurance status, marital status, household income, household size, social cohesion and safety, social support), behavioral factors (body mass index, current smoking, alcohol consumption, physical activity, recreational drug use), psychological traits and other psychosocial constructs, chronic stress factors (related to work, marriage, finances, caregiving, discrimination; perceived stress; and childhood adversity), and biological stress measures (baseline angiotensin II, epinephrine and norepinephrine, BP, heart rate, endothelin-1, and cortisol; and change in these measures with stress). Given the large number of predictors being examined, we will apply a false discovery rate of 0.05 (rather than ignore the inflated risk of Type I errors or use the excessively conservative Bonferroni correction), and interpret the results as "hypothesis generating" rather than "confirmatory".

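### Aim 1 could add one sensitivity model with baseline laboratory sodium excretion, because no planned analysis can show whether an association with change partly reflects starting level

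*Protocol*

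**What the plan says.** The Primary Aim 1 predictor is the change in urinary sodium excretion rate with stress, and the outcome is the awake-to-sleep ratio of sodium excretion rate. The primary test is "The statistical significance of the coefficient for the change in urinary sodium excretion rate with stress in this adjusted model". The fixed covariates are "age, sex, race/ethnicity (non-Hispanic whites, non-Hispanic blacks, Hispanics, and other), and body mass index", and the SAP repeats them.

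The protocol adds: "Sensitivity analyses will be performed to assess whether the strength of the association changes when additional covariates are included". The candidates named are clinic SBP/DBP, parental history of hypertension, fasting glucose and 24-hour creatinine clearance, each screened at p<0.10 against the outcome.

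Under Missing Data and Secondary Aim (protocol section 4) the predictor is labelled stress-induced sodium excretion. The Secondary Aim describes the hypothesis as a "tendency for those with lower stress-induced sodium excretion rate to have a lower daytime-to-nighttime ratio of urinary sodium excretion rate".

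The baseline value exists. Protocol section 2 states: "Urinary volume, electrolytes, creatinine, and endothelin-1 will be measured at baseline, post-stress, and recovery".

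**The concern.** A change from baseline contains the baseline value. A small change can mean a weak response to the stress tasks or a high starting level. If the awake-to-sleep ratio is itself related to starting level, the change coefficient picks up part of that relation. With post-stress SD not much larger than baseline SD, a negative baseline-outcome correlation inflates the coefficient and a positive one masks a true association. The direction reverses once the SD ratio times the baseline/post-stress correlation exceeds 1.

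What is at stake is the wording of the conclusion. The planned test can support a statement that change is associated with the ratio. Without a look at baseline, a reader cannot tell how much of that belongs to the response to stress that the label suggests.

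**Working it through.** **The plan's own figure.** For r = 0.20, two-sided 5% and 80% power, Fisher's z gives n = ((1.960 + 0.842)/atanh(0.20))² + 3 = 193.97, so 194 as stated. The sample size is not in question.

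**Is baseline in any Aim 1 analysis?**
- Fixed covariates: age, sex, race/ethnicity, BMI. No.
- Screened candidates: the measures listed above. No.
- Generalized additive model: non-linearity only. No.
- Additional Exploratory Analyses: social determinants, and sex and race/ethnicity interactions. No.
- EMA model (protocol Secondary Aim; SAP secondary analyses): EMA rating, change and their product. No.

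24-hour sodium excretion and FENa are covariates for Aim 2 only.

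**Inputs for size.** From the plan: n = 200 and r = 0.20. Everything else is assumed: change = post-stress minus baseline; k = post-stress SD / baseline SD; ρ = baseline/post-stress correlation, 0.3 to 0.7; r_B = baseline-outcome correlation, 0.1 to 0.3 in absolute value. The six covariate degrees of freedom (1 + 1 + 3 + 1) are treated as unrelated, which leaves an effective n of 200 − 6 = 194.

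**Case A: the outcome depends on baseline only.**

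corr(change, outcome) = r_B × (kρ − 1)/√(1 + k² − 2kρ)

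| k | multiplier at ρ = 0.3 / 0.5 / 0.7 | change-only test significant, abs(r_B) 0.1-0.3 |
|---|---|---|
| 1 | −0.592 / −0.500 / −0.387 | 8-70% |
| 1.5 | −0.359 / −0.189 / +0.047 | 5-32% |
| 2 | −0.205 / 0 / +0.270 | 5-20% |

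With baseline added, the change coefficient is significant in about 5% throughout (simulation, 20,000 replicates per cell). With r_B = 0 the change-only test is also at about 5%.

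One cell by hand: k = 1, ρ = 0.5, r_B = −0.3 gives a correlation of 0.15. Then atanh(0.15) × √191 − 1.960 = 2.089 − 1.960 = 0.129, a rejection rate of about 55%.

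**Against the planned r = 0.20, equal SDs.** r_B = −0.1 contributes 0.04 to 0.06 (19-30% of 0.20), and r_B = −0.3 contributes 0.12 to 0.18 (58-89%). Producing all of 0.20 needs r_B = −0.34, −0.40 or −0.52 at ρ = 0.3, 0.5 or 0.7. At k = 1.5 it needs −0.56 at ρ = 0.3 and is impossible at 0.5 or 0.7. The realistic issue is a partial contribution. With k below 1 it grows: at k = 0.8 the multipliers are −0.706, −0.655 and −0.610.

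**Case B: both voids are noisy readings of one stable level, each correlated r with the outcome.** With equal SDs, change is uncorrelated with the outcome and the planned test stays at about 5%. The partial correlation of change given baseline is r(1 − ρ)/√((1 − ρ²)(1 − r²)). At r = 0.3, ρ = 0.3 this is 0.21/0.91 = 0.231, significant in about 90%; at r = 0.1, ρ = 0.7 it is 0.042, about 9%. So here the added model is the misleading one. At k = 1.5 both models are falsely significant in the same direction in up to 42% of studies.

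**Power of the added model.** If only change matters and r = 0.20, then with c = corr(change, baseline) the partial correlation is 0.20√(1 − c²)/√(1 − 0.04c²). With equal SDs this is 0.162 at c = −0.592 and 0.185 at c = −0.387, or about 62% and 73% by Fisher's z; simulation gives about 61-74%. The primary test keeps about 80%.

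**The case against.** The strongest reply is that the change score answers the stated aim, which concerns association, and that stress-induced is simply the protocol's name for the change variable. That stands, and it is why the primary test should not move.

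Three stronger readings are tempting and are not supported:
- A reader might infer that the protocol claims an effect independent of baseline. Neither the rationale ("Individuals with lower stress-induced sodium excretion who experience psychological stress during the daytime may exhibit a shift of urinary sodium excretion") nor the Secondary Aim says so.
- A reader might see an inconsistency in the Exploratory Aim, which lists "baseline angiotensin II, epinephrine and norepinephrine, BP, heart rate, endothelin-1, and cortisol; and change in these measures with stress". There the sodium response is the outcome and these are predictors of it, so the comparison says nothing about Aim 1.
- A reader might treat baseline as the one omitted component of the predictor. Post-stress excretion is equally a component.

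Other replies also carry weight. The fixed-salt diet, fasting, water and rest may reduce baseline differences, and proportional differences in overall excretion cancel in a within-person ratio. The protocol expects substantial variability in response, which is compatible with a larger post-stress SD and a smaller problem. A high baseline that leaves little reserve could be part of the hypothesised mechanism, so adjusting for it may remove some of what is being studied. Noise is plausible: the void before the baseline period is only requested if possible, and the tasks last 10 minutes. Finally, change is never defined. A baseline-residualised change would largely remove the issue, but neither document says that is meant.

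These replies limit size and interpretation. They do not alter the fact that no planned analysis looks.

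**Conclusion.** Minor; a cheap improvement, not an error in the primary test. Both documents confirm that baseline laboratory sodium excretion is measured and used in no Aim 1 analysis. The study as planned therefore could not show whether an association with change partly reflects starting level.

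How much this matters cannot be determined from the documents. The contribution may be nil, may inflate or may mask. The rejection rates under case A illustrate what the plan would miss if baseline mattered; they do not estimate bias in this study, and they rest on assumed SDs and correlations and on change being a simple difference.

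**What to change.** Keep the change-score model as the primary analysis. Add to the Aim 1 sensitivity analyses one model that includes baseline laboratory sodium excretion rate, not subject to the p<0.10 screen. Report both change coefficients with 95% CIs, the baseline and post-stress SDs, their correlation, and the correlation of baseline with the awake-to-sleep ratio. State how change was calculated.

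Use the model as a one-way check. If the coefficient shrinks materially or changes sign, describe the result as an association with change that may reflect baseline level. Do not treat agreement, or a significant adjusted coefficient alone, as confirmation, because of case B. Any cut-off is illustrative. Flagging an adjusted coefficient below half the primary one, or of opposite sign, would catch 0-3% of significant results when a stress-only effect of r = 0.20 is true. Under case A with equal SDs it would catch 8-28%, 38-67% and 74-90% at abs(r_B) of 0.1, 0.2 and 0.3. Under case B at k = 1.5 it flags only 0-2%.

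A matching EMA model with baseline and baseline-by-EMA terms is optional.

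Cost: one extra model on data already collected, with the primary test and sample size unchanged. The added model has lower power (about 61-74% at true r = 0.20 with equal SDs) and cannot settle the question under measurement error. The SAP is written in the past tense; if the analyses have been run, label the model post hoc.

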Data Preparation: All variables will be reviewed for outliers and internally inconsistent values. Once a valid, final data set is compiled, variable distributions will be evaluated for non-normality and data transformations will be applied as needed. Winsorization may be employed to reduce the effect of extreme, but valid, observations on data analyses. Although transformed data will be used for primary inferential analyses, the description of data will feature the original (untransformed) metric for ease of interpretation.

Missing Data: Given the reasons for missing data (i.e., laboratory error or equipment failure), missing data for our primary variables will likely conform to a "missing completely at random" (MCAR) pattern. However, we will use the less restrictive "missing at random" (MAR)-analytic techniques (e.g. mixed effects regression, multiple imputation) for the analyses. For those who are missing a small number of items used to construct a psychosocial scale, we will use the EM algorithm in SAS' PROC MI procedure to estimate the expected scale score for these participants conditional on their responses to all the other

items; this is the best estimate, assuming MAR, of their scores. Although we anticipate few missing data for the primary variables (i.e. stress-induced sodium excretion, *diurnal* patterns of sodium excretion and BP) as 100% of the participants in the SABRE pilot study had complete data, we have conservatively allowed for approximately 5% (N=11) of the 211 enrolled participants to have some missing data. A minimum sample size of 200 participants without missing data will provide adequate power for testing our primary hypotheses.

Fidelity Checks: VAS stress ratings will be collected before and after laboratory stress induction. VAS stress ratings will be monitored during the conduct of the study to ensure that the manipulation (i.e. mental stress tasks) is having its intended effects. If the stress tasks are not having their intended effects, [name] will work with the research staff to bolster the dose of the experimental manipulation that is administered. The focus of these fidelity checks will be on the magnitude of the pre-/post-stressor change in VAS ratings rather than on the statistical significance of the effects (which may be limited by sample size). The research coordinator will be blinded to the VAS stress ratings.

Analytical Approach for Each Aim:

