Stress, Salt Excretion, and Nighttime Blood Pressure NCT03636490 Last IRB approval date: 01/07/2025

Statistical analyses

Participant characteristics for the analytic sample were summarized as mean and standard deviation (SD) for continuous variables and percentages for categorical variables. As a fidelity check of the mental stress tasks, we examined the pre-/post- change in VAS stress rating in the laboratory session.

To determine the association between urinary sodium excretion rate with stress in the laboratory and awake-to-asleep ratio of urinary sodium excretion over a 24-hour period, standard regression analysis as used in unadjusted and adjusted models. We have *a priori* selected the following covariates for adjustment in a multiple regression model: age, sex, race, and ethnicity (non-Hispanic whites, non-Hispanic blacks, Hispanics, and other), and body mass index. Age, sex, and race/ethnicity are standard covariates in studies of hypertension given their well-known associations with BP. Body mass index was included as a covariate since it is associated with both lower stress-induced sodium excretion and lower daytime-to-nighttime ratio of urinary sodium excretion rate. Prior data has indicated that higher clinic SBP, higher clinic DBP and parental history of hypertension are associated with lower stress-induced sodium excretion. Further, blood glucose and 24-hour creatinine clearance are associated with lower daytime-tonighttime ratio of urinary sodium excretion rate. Each of these were evaluated as candidate covariates by selecting those that are associated with awake-to-sleep ratio of urinary sodium excretion rate at p<0.10.

To determine the association between awake-to-asleep ratio of urinary sodium excretion and SBP dipping over a 24-hour period, standard regression analysis was also used in unadjusted and

adjusted models. The *a priori* covariates that were included in adjusted models are age, sex, race, ethnicity, body mass index, current smoking, alcohol use (none, moderate, heavy), blood glucose, 24-hour sodium excretion, 24-hour potassium excretion, 24-hour creatinine clearance, and FENa. In addition to age, sex, and race/ethnicity, the other measures were chosen as covariates as prior studies indicate they may confound the association between the diurnal pattern of sodium excretion and the diurnal pattern of BP. These analyses were repeated by replacing SBP dipping with DBP dipping.

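### The stated minimum of 194 matches a no-covariate calculation; at the target of 200 the adjusted Aim 1 test just reaches 80% power and the adjusted Aim 2 test has about 78%

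*Protocol*

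**What the plan says.** The protocol (section 4, Sample Size and Minimum Detectable Effect Sizes for Primary Aims) says the sample size was chosen for "80% power to detect a bivariate/partial correlation between the primary predictor and outcome of r=0.20 or greater". It then gives a single figure for both aims: "The minimum sample size required to detect this effect size with power 80% is 194 with valid data for the three primary measures". It adds: "We are targeting a final minimum sample size with complete data of 200". The Missing Data paragraph reaches 200 by allowing about 5% (11) of 211 enrolled to have some missing data, and treats 200 as adequate for the primary hypotheses.

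The primary tests are defined just before that. For Aim 1, the statistical significance of the stress-change coefficient "in this adjusted model will constitute the primary test of the hypothesis". The covariates are age, sex, race/ethnicity in four groups, and body mass index. For Aim 2 the protocol says: "The same approach for Hypothesis 1 will be used for the analysis of this hypothesis". Its covariate list is longer. It adds 24-hour sodium and potassium excretion, 24-hour creatinine clearance, FENa, and "current smoking, alcohol consumption, and fasting blood glucose". The SAP's Aim 2 list includes "age, sex, race, ethnicity, body mass index, current smoking, alcohol use (none, moderate, heavy), blood glucose", so alcohol has three levels there, and race and ethnicity appear as separate entries.

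The sample-size paragraph gives no formula, alpha, sidedness or covariate count. The only alpha is the 0.05 significance level at the end of the SAP, with no statement of sidedness.

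**The concern.** One number is offered for two kinds of test. An unadjusted correlation and a partial correlation of the same size do not need the same number of participants once covariate degrees of freedom are counted, and the two aims have covariate lists of different length. The protocol makes the adjusted coefficient the primary test, so the adjusted figure is the one that matters.

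As written, a reader cannot tell which test 194 refers to. Nor can the reader see that, at a common correlation of 0.20, Aim 2 needs more participants than Aim 1. The practical stake is modest. It is greatest if Aim 2 gives a null result and a reader takes the study to have had 80% power at exactly 0.20.

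**Working it through.** **Inputs**

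- Correlation 0.20, power 80%, stated minimum 194, target 200: protocol, sample-size paragraph.
- Enrolment 211: protocol, sections 2 and 4.
- Alpha 0.05: SAP, last line. Two-sided testing is assumed.
- Aim 1 covariate parameters: age 1, sex 1, race/ethnicity 3 (four groups), body mass index 1. So k = 6.
- Aim 2 covariate parameters: those 6 plus seven more variables. So k = 13 with alcohol as one term, or k = 14 with the SAP's three alcohol levels. This takes race/ethnicity as one four-level factor.

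**Formulas (Fisher's z, k covariate parameters partialled out)**

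- N = ((1.960 + 0.842) / atanh(0.20))² + 3 + k
- Power = Φ(√(N − k − 3) × atanh(0.20) − 1.960)

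**Reproducing 194.** With atanh(0.20) = 0.2027, the squared ratio is 190.97. At k = 0, N = 190.97 + 3 = 193.97, which rounds up to 194. One-sided 0.05 would give 154, so two-sided is the reading that fits.

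**Same formula with the planned covariates**

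| Test | k | N for 80% | Power at 194 | Power at 200 | Power at 211 |
|---|---|---|---|---|---|
| Unadjusted | 0 | 194 | 80.0% | 81.2% | 83.2% |
| Aim 1 adjusted | 6 | 200 | 78.7% | 80.0% | 82.2% |
| Aim 2 adjusted | 13 | 207 | 77.2% | 78.5% | 80.8% |
| Aim 2 adjusted | 14 | 208 | 77.0% | 78.3% | 80.6% |

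Worked example, Aim 2 with k = 14 at 200: √183 × 0.2027 − 1.960 = 0.783, and Φ(0.783) = 78.3%.

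**Detectable correlation at 200 with 80% power.** tanh(2.802 / √(197 − k)) gives 0.200 for k = 6, 0.2036 for k = 13 and 0.2042 for k = 14.

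**If race and ethnicity enter Aim 2 separately.** Assuming this adds 1 to 2 parameters (k = 15 to 16), the need is 209 to 210. Power is then 77.9 to 78.1% at 200 and 80.2 to 80.4% at 211.

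**Check on the approximation.** An exact calculation with a random predictor (noncentral t averaged over the predictor's sum of squares) needs 193, 199, 206 and 207 for k = 0, 6, 13 and 14. Each is one below the Fisher value, so the pattern does not come from the approximation.

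**Other convention.** A fixed-predictor F test with noncentrality N × f², where f² = 0.04 / 0.96 = 0.0417, needs 191 whatever the covariate count from 0 to 14. It gives 80.7% at 194 and 81.9% at 200 for either adjusted test.

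**The case against.** Four points can be made for the plan.

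First, the study aims to analyse 200, not 194. This stands. At 200 the Aim 1 test has 80.0% power, so Aim 1 has no shortfall at the target, only no margin. What remains is 7 to 8 participants for Aim 2.

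Second, the finding depends on convention. Under the fixed-predictor calculation 194 is enough for both adjusted tests. This also stands as a caveat. But that method does not produce 194, and the predictors here are measured excretion rates, not values set by design. The method that does produce 194 is the one under which it falls short. Attributing that method to the sponsor is still an inference from one matching integer.

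Third, 0.20 is described as conservative. The pilot correlations are 0.25 (Aim 1) and 0.30 (Aim 2). Taken as partial correlations, which is an assumption, Fisher power at 200 is about 94% for Aim 1 and 98.7% for Aim 2, and the N for 80% is about 130 and 98 to 99. So Aim 2 needs more participants than Aim 1 only when both are set at 0.20.

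Fourth, 200 counts people with all three primary measures, whereas Aim 2 uses two of them. The protocol also plans "analytic techniques (e.g. mixed effects regression, multiple imputation) for the analyses", so the number analysed for Aim 2 may lie between 200 and 211.

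A reader might infer that the study is underpowered, or that 194 was miscalculated. The documents support neither. Enrolment of 211 exceeds every requirement computed above, and 194 is correct for an unadjusted correlation. The fault is that the word partial extends it to tests with covariates.

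**Conclusion.** The point holds as a small misstatement. Under the only method tried that reproduces 194, that figure gives 80% power for the unadjusted correlation alone. The adjusted primary tests need 200 for Aim 1 and about 207 to 208 for Aim 2. At the target of 200, the deficit is confined to Aim 2 and is about 1.5 to 1.7 percentage points (78.3 to 78.5% against 80%). Put another way, Aim 2 has 80% power at a correlation of about 0.204 instead of 0.200. With all 211 analysed it has about 81%.

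This rests on Fisher's z with two-sided 0.05, on counting covariate degrees of freedom with predictors treated as observed, and on race/ethnicity as one four-level factor. The arithmetic is firm; the method and sidedness are inferred. Nothing here calls for a larger sample or casts doubt on the design.

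**What to change.** In the protocol's sample-size paragraph, or in the sample-size statement of the report, keep the existing sentence with its condition on the three primary measures and label 194 as the figure for an unadjusted correlation. Then add:

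> For the covariate-adjusted primary tests (Fisher z, two-sided 0.05, counting covariate df), 80% power at partial r=0.20 needs 200 for Aim 1 and about 207–208 for Aim 2; with 200 analysed, Aim 2 has about 78% power.

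The sponsor should first confirm the formula and sidedness actually used. If they differ, the added figures should be recomputed on that basis. The sponsor should also settle the coding of alcohol and of race and ethnicity in the Aim 2 model, because that fixes the covariate count.

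The cost is a label and one sentence, with no change to enrolment or analysis. The downside is that the stated position for Aim 2 becomes slightly less favourable.
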